5.3.1.3. Pregnancy

Scopolamine HBT is a Category C investigational product. Risks to unborn babies are unknown at this time; pregnant females will be excluded from this study. Female subjects should not become pregnant for at least 30 days after dose administration.

5.3.1.4. Lactation

Risks to nursing infants are unknown at this time; breastfeeding females will be excluded from this study.

5.3.1.5. Reproductive Health

The effects of Scopolamine HBT on the reproductive health of men and women are unknown. Appropriate contraceptive measures will be required for females of childbearing potential and men whose female partners are of childbearing potential.

Females of childbearing potential must have been using adequate contraception for at least 3 months prior to drug administration and must agree to use an adequate method of contraception for at least 30 days following drug administration.

For this study, adequate contraception for females of childbearing potential is defined as a male partner using condoms with spermicide or the use of one of the following methods:

- Cervical cap or diaphragm with spermicidal gel, cream or foam,
- Hormonal contraceptives (oral, implant, injection, patch, or vaginal ring), or
- Intrauterine devices.

Females of nonchildbearing potential are also eligible, defined as a subject who is postmenopausal (continuous amenorrhea for 24 months) or surgically sterile (bilateral tubal ligation, bilateral oophorectomy, or total hysterectomy). There are no contraceptive requirements for females of nonchildbearing potential.

Males with female partners of childbearing potential must agree to use adequate contraception from screening, throughout the study period, and for 30 days after drug administration. Adequate male contraception is defined as male condoms with spermicide.

5.3.1.6. Venipuncture

Blood sampling carries a minimal risk of minor discomfort and the possibility of minor bruising at the site of the needle puncture, and the possibility of lightheadedness and fainting. Rarely, there is also the possibility of infection at the needle puncture site or inflammation of the vein.

5.3.1.7. Allergic Reaction

As with any investigational new drug (IND) product administration and no matter what precautions are taken, there is always the risk of a serious, or even life-threatening, allergic reaction. Medical emergency equipment will be available at the study site to handle emergencies, such as anaphylaxis, angioedema, bronchospasm, and laryngospasm. A crash cart will be located in close proximity to the treatment room where subjects are residents.

5.3.1.8. Unknown Risks

As with all research, there is the remote possibility of risks that are unknown or that cannot be foreseen based on current information.

5.3.2. Alternatives to This IND Product or Study

At this time, atropine and 2-PAM are the only approved nerve agent treatments. Scopolamine HBT is being evaluated as a potential therapeutic to treat muscarinic symptoms and as an adjunct therapeutic to increase survival from lethal exposure to chemical warfare nerve agents.

An alternative is not to participate in this study.

5.3.3. Intended Benefit for Subjects

There is no benefit to subjects participating in this study. Payment for participation in this study is not a benefit and should not be presented as such. However, potential subjects can be told that study results may provide information required for the marketing of a new or improved product. Results of this clinical investigation will inform follow-on animal efficacy studies and a Phase 2 human clinical study of Scopolamine HBT dosing by confirming the PK upon IM administration.

PK data are key to determining the efficacious dose of Scopolamine HBT for these future studies.

5.3.4. Risks to the Study Personnel and the Environment

The principal risk in the clinical setting is in the handling of needles that may be contaminated and the attendant risks including hepatitis, human immunodeficiency virus (HIV), and other human pathogens. Adherence to standard operating procedures (SOPs) for working with infectious agents and universal precautions will reduce the risk of exposure.

There are no known risks to the environment other than those associated with the generation of biohazardous waste. All biohazardous waste will be disposed of as stipulated by local, state, and federal regulations and in accordance with study site SOPs.

5.4. Route of Administration, Dosage Regimen, Treatment Period, and Justification

Up to 240 subjects will be consented and screened for participation in the study.

This is a double-blinded, randomized, placebo-controlled, in-clinic, Phase 1, single-dose, IM, sequential dose-escalation study in healthy adults aged 18-55. Healthy volunteers will be assigned to 1 of 5 cohorts of Scopolamine HBT dosage groups: 0.005, 0.007, 0.011, 0.014, or 0.021 mg/kg, or receive the placebo, administered by IM injection to the anterior thigh. In each cohort, 6 to 9 subjects will receive active drug and 2 to 3 subjects will receive placebo. Each cohort will have at least 3 male and 3 female subjects enrolled among the first 8 subjects in the dosing group to ensure that at least 1 male subject and 1 female subject in each dosing group receive active drug. If nonextreme dose-limiting toxicities (DLTs) are observed in any of the cohorts, 4 additional subjects, 3 active and 1 placebo, may be added to each cohort.

On the first day of dosing for each cohort, 2 subjects will be dosed (1 active and 1 placebo). Upon review of the adverse event (AE) data for both subjects at 24 hours post dose (\pm 1 hour), the principal investigator (PI) and the medical monitor will determine if it is safe to proceed with dosing the remaining 6 of the first 8 subjects.

5.5. Compliance Statement

The study will be conducted according to the protocol and in compliance with International Council for Harmonisation of Technical Requirements for Pharmaceuticals for Human Use (ICH) Good Clinical Practice (GCP), Belmont Principles, and other applicable regulatory and DoD requirements. All identified study personnel will be trained to perform their roles and will carry out their responsibilities in accordance with ICH/GCP guidelines and clinic site SOPs.

5.6. Study Population

Up to 60 (30 to 45 active; 10 to 15 placebo) male and female volunteers, 18 to 55 years of age, will be enrolled in 5 dosing groups (cohorts) of 8 to 12 participants each. The actual number enrolled in the study will be determined by the safety responses noted during the study.

Each of the 5 cohorts will include at least 3 male and 3 female subjects enrolled among the first 8 subjects in the cohort to ensure that at least 1 male and 1 female subject in each dosing group receive active drug.

In addition, to assure study population diversity in an 8-subject cohort, no more than 5 subjects may be enrolled from any one of these single racial and ethnic groups: American Indian or Alaska Native, Asian, Black or African American, Native Hawaiian or Other Pacific Islander, White, Hispanic/Latino, or Other. If the cohort is expanded to 12 subjects, no more than 8 subjects (2/3 of the subjects) may be enrolled from any one of the above racial and ethnic groups. A specific distribution of subject gender across racial and ethnic groups is not required.

Refer to Section [12.2](#) for a statistical justification of the sample size.

5.7. Study Site

Pharmaron, a clinical pharmacology unit established in 2006, specializes in Phase 1/2a complex clinical pharmacology research. Pharmaron occupies the fifth and sixth floors of Building 1 in the University of Maryland BioPark. This location in downtown Baltimore, Maryland, is easily accessible by public transportation and/or personal vehicle, and volunteers will receive free parking in the nearby garage.

Pharmaron has the necessary experience, personnel, and technical resources to effectively conduct the study. Resources include, but are not limited to, a dedicated recruitment department; an outpatient unit for screening and follow-up visits; 96 inpatient beds with various unit configurations; an on-site, CLIA (Clinical Laboratory Improvement Amendments)-certified clinical diagnostic laboratory; and a United States Pharmacopeia (USP) 797-compliant pharmacy. Staff includes full-time physicians, physician assistants, nurse practitioners, and nursing, regulatory, quality, laboratory, pharmacy, and clinical personnel. Physicians and nursing staff are ACLS (Advanced Cardiovascular Life Support) certified.

Subjects will be recruited from the civilian population in the Baltimore, Maryland, metropolitan area and surrounding areas. Recruitment will include data mining of Pharmaron's racially diverse database, study-specific advertising, and pre-screening of potential participants.

6. TRIAL OBJECTIVES AND PURPOSE

6.1. Primary Objective

The primary objectives of this study are:

- To characterize the safety and tolerability profile of ascending doses of Scopolamine HBT administered by IM injection, and
- To characterize the PK of ascending doses of Scopolamine HBT administered by IM injection.

7. TRIAL DESIGN

7.1. Study Endpoints

The safety of Scopolamine HBT will be assessed from:

- The occurrence, intensity, and relationship of AEs from Day 1 through Day 30
- Results of clinical laboratory tests (hematology, coagulation, serum chemistry, and urinalysis) at Day -1 (baseline) and Days 2, 3, and 8
- Clinically relevant changes or findings from physical examinations on Day -1 and Days 1, 3, and 8
- Vital signs and ECGs on Day -1, Days 1-3, and Day 8
- Injection site assessments:
 - Visual analog scales (VAS) for pain, pruritus, tingling, and numbness at pre dose, and 5, 10, 15, 30, and 45 minutes, at and 1, 1.5, 3, 5, 8, 12, 24, and 48 hours post dose, and at Day 8 ([Appendix A](#))
 - Assessment of pain, tenderness, erythema, and induration at the injection site by a physician, physician assistant, or nurse to be performed immediately after the VAS ([Appendix C](#))
- Changes in neuropsychiatric and cognitive status assessments:
 - Brief Psychiatric Rating Scale (BPRS) expended version 4.0, 24-item scale at Day -1 (baseline), at 6 (+ 2) hours post dose (timing at the discretion of the investigator or designee), 48 hours post dose (prior to discharge), and Day 8
 - Columbia-Suicide Severity Rating Scale (C-SSRS) at Day -1 (baseline) and Day 8
 - Severity of agitation or sedation using the Richmond Agitation and Sedation Scale (RASS) if AEs of general agitation or sedation are reported ([Appendix D](#))
 - Persistent cognitive effects using the Digit Symbol Substitution Test (DSST) at Day-1 (baseline), 48 hours post dose, and Day 8 (screening DSST will serve as a practice session)

The PK of Scopolamine HBT will be determined from the following parameters calculated from plasma concentration using semi-log plots with noncompartmental analysis:

- Peak plasma concentration, C_{max} ;
- Time of peak concentration, T_{max} ;
- Apparent volume of distribution, $V_d \cdot F$;
- Elimination half-life, $t_{1/2}$;
- Plasma clearance, $Cl \cdot F$;
- Area under the curve at last sampling point, AUC_{last} , and at infinity, AUC_{∞} ;
- Mean residence time (MRT); and

- Dose proportionality using $C_{max}/Dose$ and $AUC_{\infty}/Dose$

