8.1. Subject Inclusion Criteria

A subject must meet all of the following criteria to be included in the study:

1. Male or female, 18 to 55 years of age, inclusive, at the time of drug administration
2. Without clinically significant abnormalities on physical examination at screening or prior to drug administration
3. Generally healthy, as determined by medical history review, physical examination, and laboratory testing at screening and prior to drug administration
4. Must have a BMI of ≥ 19.0 and ≤ 30.0 , and weight range of 55.0 to 85.0 kg at screening or prior to drug administration
5. Must have adequate venous access and sufficient upper leg muscle tissue for drug administration
6. If female, the subject must be nonpregnant and nonbreastfeeding, and have a negative serum pregnancy test at screening and prior to drug administration
7. If female of childbearing potential, the subject must have been using adequate contraception (as defined in Section 5.3.1.5), for at least 3 months prior to drug administration and must agree to use an adequate method of contraception for at least 30 days following drug administration
8. Females of nonchildbearing potential are also eligible, defined as a subject who is postmenopausal (continuous amenorrhea for 24 months) or surgically sterile (bilateral tubal ligation, bilateral oophorectomy, or total hysterectomy)
9. A male with a female partner of childbearing potential must agree to use a barrier method of contraception (defined as condoms with spermicide) for at least 30 days following drug administration
10. If male, must not have past diagnoses of benign prostatic hypertrophy or urinary tract obstruction and must not have on screening history/review of systems symptoms suggestive of urinary tract obstruction (eg, urinary hesitancy, urgency, frequency, or nocturia)

11. Nonsmoker/tobacco/nicotine product (including e-cigarettes) user within 3 months of first dosing and must have a total lifetime exposure to cigarettes of < 15 pack-years
12. No evidence of significant neuropsychiatric disorders based on the BPRS at screening and prior to drug administration, which is defined as having a global score of ≤ 25 with no score higher than 2 on any one item, with the exception of a score of 1 (ie, Not Present) to disorientation, hallucinatory behavior, and suspiciousness (ie, paranoia)

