6.3 HYPOTHESES AND DECISION RULES

As the objective of this study is to characterize the safety and tolerability of escalating doses of Scop HBT, three sets of safety endpoints will be compared statistically between placebo and active dosing groups. Some PK parameters will also be compared statistically across dose levels. Table 7 describes the hypothesis testing pre-specified in the statistical analysis.

The null hypothesis of no worse scores for Injection Site VAS (pain, itching, tingling, numbness); change in BPRS Score (6 hours, 48 hours, 8 days); change in DSST (48 hours, 8 days); and C-SSRS (SD 8) between dose levels of active Scop HBT and placebo will be tested statistically using a one-sided alternative of worse (higher for C-SSRS, VAS, and BPRS, lower for DSST scores for Scop HBT vs. placebo). Each dose level will be tested against the same placebo group (all participants receiving placebo). Methods for analysis of neuropsychiatric scales and injection site reactions are described in Sections 6.13.4 [6.14.6](#) and [6.14.8](#), respectively.

For PK parameters, variation across doses will be tested for T_{max} , $t_{1/2}$, V_d/F , Cl_F , and MRT against the null hypothesis of no difference across doses. A joint significance test (1 test per parameter) will be used.

Dose-proportionality will be tested using the dose-normalized parameters $C_{max}/Dose$ and $AUC_{\infty}/Dose$. A likelihood ratio test will be used for testing the joint null hypothesis of equivalence across all doses using a two-sided alternative. Each dose level will also be tested against the next dose level using a two-sided test. The methods for analysis and hypothesis testing are described in Section - [6.15](#). A total of 110 hypothesis tests will be performed. Procedures for multiple comparisons are detailed in Section [6.8](#).

Table 7: Pre-Specified Hypothesis Tests

Drug Characteristic	Null Hypothesis	Relevant Endpoints [Count]	Number of Comparisons Per Parameter	Total Number of Hypothesis Tests
Safety	Equivalence with Placebo	Injection site VAS (pain, itching, tingling, numbness) x (10-45 minutes, 1-5 hours, 8-48 hours) [12] Change in BPRS score from baseline (6 hours, 48 hours, SD 8) [3] Change in DSST scores from baseline (48 hours, SD 8) [2]	5 (Each dose level vs. Placebo)	90

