6.8 ADJUSTMENT FOR MULTIPLE COMPARISONS

Section [6.3](#) specifies the hypotheses to be tested in this Phase 1 trial of the safety and pharmacokinetics of IM injection of Scop HBT. Given the large number of hypothesis tests, the Benjamini-Hochberg method will be used to determine statistical significance. As this trial is exploratory, a relatively high false discovery rate (FDR), the proportion of significant findings that are spurious, will be used. For this study, the FDR will be set at 0.20. The choice of a high FDR prevents rejecting marginally significant findings, which may provide important information about the drug's safety and pharmacokinetic properties. With 110 tests and an FDR of 0.20, the threshold for statistical significance for the five lowest p-values will be 0.0018,

0.0036, 0.0055, 0.0073, and 0.0091. Statistical significance of tests will be noted using at the alpha = 0.05 level as well as through the Benjamini-Hochberg method. Study sponsors should note that one-in-five significant findings obtained through this process are expected to be spurious.

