6.10 DISTRIBUTIONAL ASSUMPTIONS

The residuals of ANOVA models will be assessed for normality using a Shapiro-Wilk test in conjunction with visual inspection of quantile-quantile plots. Lognormality is commonly assumed for PK parameters. If the normality assumption is not met, logarithmic (natural or base-10) transformation will be assessed. If lognormality is rejected, non-parametric bootstrap replication with a minimum of 10,000 replications will be used to calculate confidence intervals and perform hypothesis testing.

With small samples, the normality of parameters, such as the sample mean, cannot be assured. Therefore, quantile-based confidence intervals will be obtained, and hypothesis testing will be conducted using comparisons of observed test statistics to test statistics obtained under the null hypothesis. For hypotheses of equivalence between two populations (e.g. placebo and dosage groups, $\beta_1 = 0, \mu_1 = \mu_2$), an unequal sample unequal variance T-statistic will be used:

$$T = \frac{\widehat{\mu}_1 - \widehat{\mu}_2}{s_p \sqrt{\frac{1}{n_1} + \frac{1}{n_2}}} \quad (1)$$

where, $\widehat{\mu}_1$ and $\widehat{\mu}_2$ are the observed sample means, and

$$s_p = \sqrt{\frac{(n_1-1)s_1^2 + (n_2-1)s_2^2}{n_1+n_2-2}} \quad (2)$$

Where s_1^2 and s_2^2 are the sample variances. The null distribution will be generated by resampling from the values at their two groups shifted to their pooled sample mean.

For joint significance tests (e.g. $H_0: \beta_1 = \beta_2 = \beta_3 = \beta_4 = 0$), the F-statistic will be used with the formula,

$$F_b = \frac{\left(\frac{RSS_1 - RSS_2}{p_2 - p_1}\right)}{\left(\frac{RSS_2}{n - p_2}\right)} \quad (3)$$

where RSS_1 is the residual sum of squares for an ANOVA model fit under the null with p_1 parameters and RSS_2 a model fit with all parameters p_2 included. The null distribution will be generated through resampling from the distributions of each dosage cohort shifted to their common mean. With bootstrap resampling, p-values will be calculated by comparing observed values of the test statistic to the null distribution:

$$p = \frac{1}{B} \sum_{b=1}^B I(F_b \geq F_{obs} \text{ or } |T_b| \geq |T_{obs}|) \quad (4)$$

where B is the number of bootstrap samples taken.

ANOVA also assumes homogeneity of variance (i.e. homoskedasticity). Homogeneity of variance will be assessed. If variances are equal, homogenous variance ANOVA will be

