6.14.6 Neuropsychiatric Scales

Descriptive statistics (mean, standard deviation, minimum, maximum, median) of scores on the neuropsychiatric status assessments (BPRS and C-SSRS) will be presented for each timepoint by dosing group (placebo, 0.005, 0.007, 0.011, 0.014, 0.021mg/kg).

As the RASS will only be used if general agitation or sedation are reported, the number of participants with RASS performed, the reason for performance of the RASS, the time since injection when the RASS was administered, the RASS score, the resulting action taken (e.g., rescue drug administered, resolved or unresolved) will be presented by dose group and overall.

Signal neuropsychiatric events defined as DLTs (BPRS ≥ 40 or item score ≥ 4 at 48-hour post-dose evaluation) or symptoms (e.g., delirium, paranoia, and/or hallucinations) defined as adverse events will be noted and the affected participants' BPRS, C-SSRS, and RASS (if applicable) scores will be presented at each time point in relation to the determination of the event.

Change in BPRS scores from baseline (when BPRS≤25) will be compared for each dose level to placebo. Each time-point will be modeled separately. Changes in BPRS scores will be compared between each dose and the placebo group using a Wald test of coefficients from ANOVA.

Change in C-SSRS scores at SD 8 (from a baseline of zero) will be assessed. The proportion of individuals having a change in score from zero will be compared for each drug dosage level to the placebo group using Fisher's exact test. Scores for all participants receiving active Scop HBT will be compared to those receiving placebo.

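### For BPRS change, the SAP's fallback is an undefined log step and then a two-sided bootstrap of a one-sided hypothesis; correct Eq. 4 and prespecify a one-sided permutation test

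*Protocol*

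**What the plan says.** - **Scale and eligibility.** Protocol 7.1 uses the "Brief Psychiatric Rating Scale (BPRS) expended version 4.0, 24-item scale at Day -1 (baseline), at 6 (+ 2) hours post dose", then at 48 hours and Day 8. Inclusion criterion 12 (Protocol 8.1) asks for no significant disorder, "which is defined as having a global score of ≤ 25 with no score higher than 2 on any one item". It tightens this "with the exception of a score of 1 (ie, Not Present) to disorientation" and two other items, which also shows that an absent symptom scores 1.
- **Planned test.** SAP 6.14.6 models each time point separately: "Changes in BPRS scores will be compared between each dose and the placebo group using a Wald test of coefficients from ANOVA". SAP 6.3 compares each dose with placebo pooled over all cohorts, and the null hypothesis "will be tested statistically using a one-sided alternative of worse" scores on active drug.
- **Fallback.** SAP 6.10 checks residuals with Shapiro-Wilk. "If the normality assumption is not met, logarithmic (natural or base-10) transformation will be assessed". Then: "If lognormality is rejected, non-parametric bootstrap replication with a minimum of 10,000 replications will be used". The two-group bootstrap shifts each group to the pooled mean, resamples, and computes a T statistic (Eqs. 1-2). Its p-value (Eq. 4) counts resamples in which the absolute value of T is at least the absolute observed value.
- **Decision rule.** SAP 6.8 reports significance at 0.05 and also by Benjamini-Hochberg over 110 tests with a false discovery rate of 0.20: "the threshold for statistical significance for the five lowest p-values will be 0.0018", rising to 0.0091 for the fifth.

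No rank or permutation test is planned for BPRS, although C-SSRS receives Fisher's exact test. Protocol 12.5 describes a different fallback (link functions, bootstrap standard errors, robust errors), but SAP section 1 says the SAP prevails.

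**The concern.** BPRS change has a hard lower bound next to its baseline and is open upwards. Residual normality is then unlikely to hold, so the fallback matters more here than the ANOVA. Its first step cannot be run on a change of 0 or -1. Its second step answers a two-sided question, while the hypothesis is one-sided.

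The two-sided form costs more than a doubling of p. When a small, right-skewed active group is resampled, draws that miss the large values have a low mean and a small variance together. They give large negative values of T, which say nothing about worsening but are counted by Eq. 4. Neuropsychiatric toxicity is an expected effect of this drug, and BPRS change supplies 15 of the 110 tests (3 times x 5 doses). A dose with clear worsening could be reported as non-significant because of the test rather than the data.

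**Working it through.** **1. Bound on change (documents only).** Lowest total = 24 items x 1 = 24. The cap is 25, so baseline is 24 or 25 and change is at least 24 - 25 = -1. The log of a change of 0 or -1 does not exist.

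**2. The SAP's own thresholds.** k x 0.20/110 for k = 1 to 5 gives 0.0018, 0.0036, 0.0055, 0.0073, 0.0091, as stated. The threshold reaches 0.05 at k = 0.05 x 110/0.20 = 27.5, so about 28 rejections are needed before it is as loose as 0.05.

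**3. Worked example (invented data, planned sizes).** Active changes 0, 1, 3, 6, 12, 20; placebo eight 0s, 1, 2.
- Means 42/6 = 7 and 3/10 = 0.3; difference 6.7.
- Sums of squares 296 and 4.1; s_p = sqrt(300.1/14) = 4.63; T = 6.7/(4.63 x sqrt(1/6 + 1/10)) = 2.80.
- Permutation: of C(16,6) = 8,008 splits, 31 give an active sum of 42 or more. The non-zero values total 45, so those left out may sum to at most 3: one of 1, 1, 2, 3 left out (4 splits), or a pair 1+1, 1+2, 1+2 left out with one of nine zeros taken in (27 splits). p = 31/8,008 = 0.0039.
- Bootstrap (200,000 resamples): one-sided p = 0.019; Eq. 4 as written p = 0.12. The difference, about 0.10, is the irrelevant negative tail.

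**4. Power (assumed distributions).** Placebo change 0/1/2/4 with chance 80/12/5/3%. Active change 0/1/3/6/12/20 with chance 10/15/20/20/20/15%, mean 0.15 + 0.6 + 1.2 + 2.4 + 3.0 = 7.35. Six active against ten placebo:

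| Level | Bootstrap as written | Bootstrap, one-sided | Permutation, one-sided |
|---|---|---|---|
| 0.05 | 31% | 95% | 98% |
| 0.0091 | 2% | 24% | 83% |

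Repeat runs differ by one or two points.

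**5. A second, separately chosen set.** A share of active subjects rises by 8 on average with skew, 5% of placebo subjects rise by 3 on average, and 20% score 25 by chance. The order of columns is as above.

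| Sizes, share rising | At 0.05 | At 0.0091 |
|---|---|---|
| 6 vs 10, 70% | 22 / 82 / 85% | 3 / 17 / 56% |
| 6 vs 10, 85% | 42 / 94 / 96% | 9 / 39 / 82% |
| 9 vs 15, 70% | 52 / 98 / 97% | 10 / 68 / 87% |

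A true unequal-variance statistic changed little: at 70% rising, 6 vs 10 and 0.05, the one-sided bootstrap gave 82% either way. Across the simulated settings Shapiro-Wilk rejected normality in 87-100% of trials.

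**6. Error rate with no drug effect and exchangeable cohorts** (6 vs 10, 15% rising in every group, nominal 0.05): as written 0.8%, one-sided bootstrap 4.4%, permutation 2.8%.

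**7. Error rate if cohorts are not exchangeable.** Let 40% rise in both arms of cohort 5 and 5% elsewhere. At 0.05: as written 2%, one-sided bootstrap 21%, permutation 21%. At 0.0091: 0%, 0.8% and 5.2%.

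**8. Permuting only within a cohort's blocks** (SAP 3.6). 2 x 6 = 12 arrangements with 8 subjects, so the smallest p is 1/12 = 0.083. With 12 subjects, 2 x 6 x 4 = 48, and the smallest p is 1/48 = 0.021.

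**The case against.** **The gap depends on the threshold.** Correct. Once Eq. 4 is one-sided, little separates the two tests at 0.05. A reader might infer that the bootstrap method itself misses clear effects at every level; the figures do not support that. Benjamini-Hochberg also loosens as other tests reject. With the procedure run over 110 tests under assumed effects, one-sided bootstrap against permutation at the top dose was 0.09 vs 0.74 with no other true signal, 0.81 vs 0.93 with ten, and 0.94 vs 0.96 with twenty.

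**The bootstrap may never be reached.** SAP 6.10 says only that a log will be assessed. With an offset, log(change + 2) in the worked example passes Shapiro-Wilk (p = 0.08) and a one-sided t-test gives p = 0.0016. In the second set of distributions both normality checks failed in only 15-64% of trials with a drug effect. This stands, but the SAP names no offset, and choosing one after seeing data is what prespecification should prevent.

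**Permutation is not unconditionally exact.** This stands. Randomization is within small blocks in each cohort, while the comparison uses placebo pooled over sequential cohorts. Step 7 shows the cost if cohorts differ, and at 0.0091 permutation suffers more than the one-sided bootstrap. The pooled-placebo comparison already makes the exchangeability assumption, so it must be stated whichever test is used.

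**The importance is limited.** SAP 6.1 calls the analysis mainly descriptive, SAP 6.8 calls the trial exploratory, and the DSMB uses no statistical test. A 48-hour BPRS total of 40 or more, or any item at 4 or more, is a DLT in its own right. Dose escalation is therefore untouched. BPRS data after rescue are censored (SAP 6.11), which may remove the largest rises; no choice of test repairs that.

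**Conclusion.** The point holds. The bound at -1, the undefined log and the mismatch between Eq. 4 and SAP 6.3 follow from the documents alone. The skew and the pile-up at zero are likely but assumed: eligibility fixes the baseline, not the change. All power figures rest on assumed distributions; two different sets agree in direction.

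At 0.05 the loss is large (31% against 95-98%) and comes almost wholly from the two-sided Eq. 4. The added value of permutation is at the stricter ranks (24% against 83% at 0.0091) and shrinks when many other tests are significant. Three stronger readings are not supported: that the planned bootstrap inflates false positives (as written it is conservative), that a permutation test controls error whatever happens between cohorts, and that the same replacement is shown to be needed for injection-site VAS, for which no simulation was done. The matter affects the reported safety comparisons and should be corrected before unblinding.

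**What to change.** 1. **SAP 6.10, Eq. 4.** Make the p-value one-sided, in the stated direction of harm, wherever SAP 6.3 sets a one-sided alternative. This includes VAS and DSST.
2. **SAP 6.14.6.** For BPRS change, drop the log step. Prespecify a one-sided permutation test of the mean difference, each dose against pooled placebo, at 6 hours, 48 hours and Day 8, and report the mean difference as the estimate. The 110-test family is unchanged.
3. **State the assumption.** Error control requires placebo subjects to be exchangeable across cohorts. Add a cohort-stratified sensitivity analysis, and say that with 8 subjects its smallest attainable p is 1/12, so it can show consistency but not significance.

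Leave the VAS method otherwise as it is. The cost is about one SAP paragraph and a few lines of code. The downside is that power at 0.05 may be a few points lower than with the one-sided bootstrap in expanded cohorts (97% against 98% in step 5, and up to 3-4 points in other settings). Discreteness is no obstacle: at 6 against 10 the smallest possible p is 1/8,008.
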